7.6.5. Clinical Laboratory Tests

Laboratory safety assessments will be collected at every clinic visit throughout the study to monitor subject safety. Clinical laboratory tests are listed in [Section 12.2](#) will be collected per the schedule listed in [Table 1](#) and [Table 2](#). These clinical laboratory assessments will include CBC with automated differential, creatinine, blood urea nitrogen, and eGFR calculation, comprehensive metabolic panel, as well serum pregnancy test for all women of childbearing potential.

The following liver function and eGFR tests will be monitored throughout the study as follows.

- If AST or ALT increases > 3 times ULN during the study, subject should be followed with weekly laboratory repeat testing and continue in study if levels trending down. Subject will be discontinued if levels do not decline to under 3 x ULN.
- If total bilirubin increases to 1.5 x ULN or more during study, the subject will be discontinued.

- Subjects with significant renal insufficiency, eGFR < 30 mL/min (calculated using the Cockcroft-Gault formula or Pediatric GFR calculator or Bedside Schwartz) will be discontinued if the criterion is met post baseline.

If any of the criteria above are deemed clinically significant by the investigator, then the sponsor's medical monitor should be contacted.

Due to the difficulty in obtaining urine samples, urinalysis will be conducted at Visit 1 (screening) or baseline (Visit 2), Week 17 (Visit 5), Week 52 (Visit 9), and annually thereafter or at the safety follow up visit if investigational product is discontinued. An attempt will be made to collect a urine sample at screening in order to perform the study-related urinalysis. Otherwise, the urine sample for the urinalysis can be collected at baseline.

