## 2.3 Time Windows for Analysis

For by-visit safety or efficacy summaries, only scheduled visits will be analyzed. But if subjects prematurely discontinue from the study and complete assessments at the Taper Visit, then that visit may be reassigned to another visit for analysis purposes, as described in subsequent sections, including [Section 7.1.1](#).

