### 7.1.1 Handling of Missing Data

The primary analysis will use all available data. Careful educating and monitoring of the study sites will attempt to limit the amount of missing data to nearly zero, but despite these efforts, some missing data may still arise. Thus a sensitivity analysis, in which the missing data will be replaced, will be performed on the primary efficacy endpoint; see [Section 7.1.8](#).

When an item from a secondary or efficacy endpoint is missing, then so will any subscales or totals that include it.

When subjects prematurely discontinue from the study they are asked to complete the non-seizure assessments at the Taper Visit. For analysis purposes, their data from the Taper Visit will be reassigned to the first visit at which the assessment is scheduled subsequent to the discontinuation and the scheduled day is within 32 days of the Taper visit. For example if a subject completed Visit 3 and then prematurely discontinued and completed assessments at the Taper Visit on Study Day 100, then the Taper visit would be reassigned to Visit 5 (Week 17) for analysis purposes since Visit 5 is scheduled for Study Day 120, 20 days after the assessments were actually completed. (Although the first visit after Visit 3 is Visit 4 (Week 9), that visit is scheduled on Study Day 64, which is not within 32 days of Study Day 100.) But if the Taper Visit assessments were completed on Study Day 28 then the Taper visit would not be reassigned to a regular study visit since Study Day 28 is not within the 32-day window of any scheduled visit. Taper Visit assessments that are not reassigned will not be included in the tabulations but will be included in the data listings.

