## 9. SAFETY ANALYSIS

All safety analyses will be performed in the Safety Population. The results in the DB and OLE phases will be summarized separately. In both phases, the results will be summarized by the DB treatment actually received and, for the OLE phase of the study, combined over the treatment groups.

The number and percentage of days that subjects received study drug, the highest percentage of the maximum allowable daily dose (1800 mg or 63 mg/kg) that subjects received, and the total amount of study drug received will be summarized. The denominator for the percentage of days of study drug is the number of days in the phase. If the subject stops taking drug during the phase then the last day that drug was taken will be used for the last day of the phase, and if the subject is ongoing in the phase then the last known treatment date will be used. For the OLE phase, the number and percentage of days that subjects received study drug will be summarized over just the OLE phase as well as over the entire study (combined DB and OLE phases) but the classification by the DB treatment applies only for the OLE phase summary. The summarization over the entire study will include the DB data only from subjects who were in the GNX group during the DB phase, regardless of whether they entered the OLE, and all the subjects from the OLE phase

A subject data listing will be provided with full details of the study drug dispensation.

Safety assessments include:

- AEs
- Clinical laboratory tests
- Vital signs including temperature, blood pressure, pulse rate, and weight
- 12-lead ECG
- Physical, neurological and developmental examinations
- Tanner staging (OLE phase only)
- Concomitant AED levels

Baseline is defined as the last non-missing value obtained before the first DB treatment.

Assessments performed at multiple post-baseline time points will be summarized at each time point for which they are scheduled, but the listings will also include any assessments performed at unscheduled time points. Assessments performed at the Taper Visit for prematurely discontinued subjects will be reassigned as described in [Section 7.1.1](#); if the assessments are not

reassigned, they will not be included in the tabulations but will be included in the data listings. Subjects who prematurely discontinue from the study are also asked to complete assessments at the Safety Follow-up Post-Taper Visit, but these will not be reassigned.

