**SBP:**

High:  $\geq 1.5 \times \text{ULN}$ ; or a  $\geq 20$  mmHg increase from baseline if clinically significant at baseline  
 Low:  $\leq 0.75 \times \text{LLN}$ ; or a  $\geq 20$  mmHg decrease from baseline if clinically significant at baseline

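### PCS and shift tables count scheduled visits only, so an abnormal value first seen at an unscheduled draw or an out-of-window Taper Visit can be missing from all of them

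*SAP*

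**What the plan says.** SAP 2.3 sets the general rule: "For by-visit safety or efficacy summaries, only scheduled visits will be analyzed". SAP 9 applies it to safety data: "Assessments performed at multiple post-baseline time points will be summarized at each time point for which they are scheduled". A qualifying clause covers the remaining values: "but the listings will also include any assessments performed at unscheduled time points".

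For subjects who leave the study early, SAP 7.1.1 reassigns Taper Visit data by this rule: "first visit at which the assessment is scheduled subsequent to the discontinuation and the scheduled day is within 32 days of the Taper visit". SAP 9 carries that rule over to safety, and says of values that fail it that, unless "reassigned, they will not be included in the tabulations but will be included in the data listings". Such subjects are also "asked to complete assessments at the Safety Follow-up Post-Taper Visit, but these will not be reassigned".

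SAP 9.2 counts laboratory categories by visit and gives shift tables by visit. SAP 9.3.1 counts vital-sign abnormalities by time point, and SAP 9.3.2 summarises ECG interpretations and shifts by visit. None of the three describes a worst-value or any-post-baseline count.

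Protocol 7.6.5 generates laboratory draws between visits. If AST or ALT exceeds 3 x ULN, the "subject should be followed with weekly laboratory repeat testing and continue in study if levels trending down".

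For SBP, DBP and pulse, SAP 9.3.1 defines PCS as passing an absolute limit or changing by a set amount. For SBP the upward change is a 20 "mmHg increase from baseline if clinically significant at baseline".

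**The concern.** Listings give no rates by arm, so a value that is only listed does not enter the comparison of GNX with PBO on fixed limits. Unscheduled and early-termination values tend to be collected because something is wrong.

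The protocol's action limits almost coincide with the PCS limits. AST or ALT above 3 x ULN triggers weekly repeats, and SAP 9.2 calls 3 x ULN or more PCS. Total bilirubin of 1.5 x ULN or more leads to discontinuation, and the same value is PCS. A subject who first reaches such a limit at an unscheduled draw could therefore leave treatment without appearing in any PCS count.

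Two further points in the same sections need attention. The Day 28 example in SAP 7.1.1 does not fit the rule it illustrates. The vital-sign change criterion also depends on a baseline condition that the SAP does not define.

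**Working it through.** **Scheduled days.** SAP 7.1.1 puts Week 9 on Study Day 64 and Week 17 on Study Day 120. Both fit 1 + 7 x week, so Week 5 is 1 + 35 = Day 36. Protocol Table 1 schedules chemistry, haematology, blood pressure, pulse and respiration at Weeks 5, 9 and 17; ECG at Weeks 5 and 17; urinalysis and weight at Week 17 only.

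**The SAP's own examples.**
- Taper on Day 100: 120 - 100 = 20, within 32; 100 - 64 = 36, outside 32. It goes to Visit 5, as the SAP says.
- Taper on Day 28: 36 - 28 = 8, within 32. The SAP says Day 28 is within the window of no scheduled visit. The example contradicts the rule for anything scheduled at Week 5.

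**Forward reading, earlier visits attended.** A Taper Visit on day d is reassigned if a scheduled day x satisfies 0 <= x - d <= 32. Visit 3 then covers Days 4-36, Visit 4 Days 32-64 and Visit 5 Days 88-120.

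| Assessment | Taper days not reassigned | Count | Share of Days 1-120 |
|---|---|---|---|
| Chemistry, haematology, BP, pulse, respiration | 1-3, 65-87 | 3 + 23 = 26 | 21.7% |
| ECG | 1-3, 37-87 | 3 + 51 = 54 | 45.0% |
| Urinalysis, weight | 1-87 | 87 | 72.5% |

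**Other readings.**
- If the window runs 32 days either side of a missed visit, the losses are Days 1-3 (3 days, 2.5%) for the first row and Days 1-3 and 69-87 (22 days, 18.3%) for ECG. The third row is unchanged.
- If the Day 28 example is taken to exclude Days 1-28, the losses are 28 + 23 = 51 days (42.5%), 28 + 51 = 79 days (65.8%) and 87 days (72.5%).

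The range is 2.5% to 72.5%, or 3% to 73% rounded. These are shares of calendar days, not of subjects.

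**AST/ALT.** If the value above 3 x ULN is found at a scheduled visit, the subject is already counted as PCS there. What is lost is a higher peak on a weekly repeat that does not fall on a scheduled visit. If the value is first found at an unscheduled draw and is below 3 x ULN by the next scheduled visit, or the subject leaves outside the Taper window, the subject is in no PCS count.

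**Vital-sign change criterion.** Over 12 years the SBP limits are 1.5 x 120 = 180 and 0.75 x 100 = 75.
- If the baseline condition means PCS in the same direction, a baseline of at least 180 plus 20 is at least 200, already above 180. A baseline of at most 75 minus 20 is at most 55, already below 75. Enumeration within each of the four age bands gives no added flags for SBP, DBP or pulse. The same holds after a move up one band. A two-band move leaves a sliver (157.5 + 20 = 177.5, below 180), but that cannot arise within 17 weeks.
- If it means the investigator's judgement, SBP 140 rising to 165 (up 25, below 180) is flagged only by the change criterion.
- If it means PCS in either direction, SBP 75 rising to 125 (up 50, above the ULN of 120, below 180) is flagged only by the change criterion.

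**The case against.** The strongest reply is that other tables already cover much of this. Abnormal values at scheduled visits are tabulated. Under Protocol 8.1.5 a clinically significant laboratory, vital-sign or ECG change can be an adverse event. Protocol 4.5 requires discontinuations due to AEs to be on the AE page, and SAP 9.1 tabulates TEAEs leading to discontinuation by arm. That stands, and it limits the harm. It does not close the gap: AE recording depends on investigator judgement, whereas PCS counts apply fixed limits.

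The Taper rule also concerns subjects who leave the study. Those who only stop drug are followed per protocol, so later visits they attend are tabulated. The stated minimum, however, is the seizure diary. The post-taper follow-up is a scheduled column in SAP Table 2, so values that are not reassigned might still be shown as their own time point; the SAP does not say.

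A reader might infer that the safety tables generally miss abnormal values, or that the omission pulls the arms toward no difference. The first is wrong, because scheduled-visit abnormalities are counted. The second is plausible but cannot be shown without dropout and unscheduled-draw rates by arm.

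A reader might also infer that the vital-sign change criterion can never add a true flag. That holds only on the same-direction PCS reading, which the SAP does not state. The QTc criterion is not affected, because its 60 msec increase carries no baseline condition.

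**Conclusion.** The gap is real and limited. Under the rules as written, a PCS value first seen at an unscheduled draw, or at a Taper Visit outside the window, can be missing from every PCS and shift table. The peak on a weekly AST/ALT repeat between visits is also untabulated.

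The day ranges rest on Week 5 being Day 36, on earlier visits having been attended and on the forward reading of the rule. Urinalysis loses Days 1-87 on every reading; the other figures move with the reading. The number of subjects affected and the size or direction of any bias are unknown.

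The vital-sign criterion needs a definition; the documents do not support replacing it. A reader might want a change limit that applies to everyone outside the normal range. Those ranges are narrow, however: over 12 years DBP is 70-80, a width of 10, so any 15 mmHg change from an in-range baseline would become PCS.

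The change is worth making before database lock. It does not touch the primary efficacy analysis.

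**What to change.** 1. In SAP 9.2, 9.3.1 and 9.3.2, add an any-post-baseline (worst value) row to each PCS and shift table. Use all on-study values in the phase: scheduled, unscheduled, Taper and safety follow-up. Keep the by-visit rows unchanged.
2. In SAP 7.1.1, reconcile the Day 28 example with the 32-day rule, and state whether the window is forward only or runs either side of a missed visit.
3. In SAP 9.3.1, say whether clinical significance at baseline means PCS or investigator judgement, and in which direction.

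The data are already collected, so the cost is SAP wording and programming. The drawbacks are a few more rows, somewhat higher counts, and some dependence of the worst-value row on how often a subject was sampled, which a footnote should state.

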## 9.1 Adverse Events

Adverse events (AEs) will be coded by System Organ Class (SOC) and Preferred Term (PT) using the MedDRA®, version 16.0 or higher. The verbatim term will be included in the AE listings. Except where indicated, the summary tables will include only TEAEs. All AEs, treatment-emergent or otherwise, will be presented in subject data listings.

A treatment-emergent adverse event (TEAE) is defined as an AE that starts or worsens on or after the first dosing day of study drug. The AE analyses for the main 17-week DB treatment phase of the study will include AEs that start or worsen during that phase and will not include AEs that start or worsen during the OLE phase; ie, they will not include any AEs starting or worsening on or after the first dosing day of the OLE phase.

For the OLE phase of the study, the AEs will be summarized over just the OLE phase as well as over the entire study (combined DB and OLE phases) but the classification by the DB treatment applies only for the OLE phase summary. The summarization over the entire study will include AEs in the DB phase only from subjects who were in the GNX group during the DB phase, regardless of whether they entered the OLE, and all the subjects from the OLE phase; i.e., it will include only the AEs following GNX exposure. The summarizations over just the OLE phase will include TEAEs that start or worsen after the first day of the OLE phase; the summarizations over the entire study will include TEAEs that start or worsen on or after the first dosing day of GNX.

The TEAEs will be summarized as the number of events and the number and percentage of subjects with TEAEs. Subjects who report the same PT on multiple occasions will be counted once for the PT: under the highest severity (severe > moderate > mild) when summarized by severity and under the closest relationship (related > unrelated) to study drug when summarized by relationship. TEAEs with missing relationships will be considered as related.

If a subject reports multiple PTs for a SOC, the subject will be counted only once for that SOC. For the counting of events, all the PTs will be included in the counts, even when subjects have multiple PTs.

Pre-treatment emergent AEs by will be summarized by SOC and PT (only for the DB period summary).

TEAEs will be summarized as below.

- An overview table of TEAEs, including number of events and number (%) of subjects with
  - TEAEs

- serious TEAEs (Treatment-emergent SAEs)
- treatment related TEAEs
- TEAEs by severity
- TEAEs leading to study drug discontinuation
- TEAEs leading to dose reduction or temporary study drug discontinuation
- TEAEs leading to death
- TEAEs by SOC and PT
- TEAE by SOC, PT, and Severity
- Study drug related TEAEs by SOC, PT
- Treatment-emergent SAEs by SOC and PT
- TEAEs leading to study drug discontinuation by SOC and PT
- TEAEs leading to dose reduction or temporary study drug discontinuation by SOC and PT
- TEAEs of special interest: rashes and the reproductive system and breast disorders system organ class
- TEAEs by PT

All AE tables will be sorted by SOC and PT in decreasing frequency of the number of subjects in the GNX group in the DB summaries and the combined groups in the OLE summaries; in case of tied frequencies, the sorting will be alphabetical.

For purposes of determining treatment emergent events, missing start and stop dates will be imputed as shown in the following table; however the actual dates, not the imputed ones, will display in the data listing.

Partial Missing Start or Stop Date	Imputed Start Date	Imputed Stop Date
Missing month, day, and year	First dose date	
Missing month and day, and the year is present	First dose date if the year is the same as the year of first dose date, else first dose date of the OLE if the year is the same as the year of the first OLE dose date, else January 1 of the AE start year.	December 31 of that year
Missing day, but year and month are present	First dose date if the year and month are the same as the year and month of first dose date, else first dose date of the OLE if the year and month are the same as the year and month of the first OLE dose date, else the 1 st of the AE start month.	Last day of that month
Missing month, but year and day are present	Assume day is also missing and impute as above	Missing month imputed as December

If an imputed start date is later than the stop date, then the stop date (after any needed imputations) will be used instead for the imputed start date.

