### 7.1 Double-Blind Phase

All efficacy analyses will be conducted in the ITT population. A supportive analysis of the primary and secondary efficacy endpoints also will be conducted in the PP population.

The estimand that is most clinically relevant as well as estimable in a manner that protects the integrity of randomization is the outcome measure (e.g., the percent change in 28-day seizure frequency), where ALL randomized subjects would be included in this analysis throughout the study period. Hence, all available data will be used, even if they were collected after the subject stopped taking study medication, regardless of whether the subject took rescue medication. [Section 7.1.1](#) details the handling of missing data.

For the analyses of seizures, the baseline phase consists of 6 weeks before the first day of treatment and the DB phase starts the day following the first day of DB treatment until the final visit for subjects who do not enter the OLE and up to the day before the first dose of OLE treatment for those who do. The first day of treatment is not in either phase since the seizures could occur both before and after the first treatment.

Tests of significance between the 2 treatment groups will be performed for the primary endpoint with a 2-sided significance level of 0.05.

Seizure diary compliance for the baseline and the post-baseline DB phase intervals will be calculated as:

$100 \times (\text{Number of Days with Available Seizure Diary}) / (\text{Last Available Seizure Diary Date} - \text{First Day of the Phase} + 1)$ .

Seizure diary compliance between visits will be calculated as:

$100 \times (\text{Number of days with available seizure data between visits}) / \text{Number of days between visits}$ , with the days between visits defined as the day of the prior visit up to the day before the current visit.

The compliances will be summarized with descriptive statistics and the percentage of subjects at least 80% compliant.

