## 7.2 Open-Label Extension

All of the analyses for the DB phase will be repeated for the OLE phase, with the following differences:

- The results will be presented overall and also classified according to the DB treatment received by the subjects
- The post-baseline seizure endpoints will be derived starting from the first dosing day of OLE treatment
- The only sensitivity analysis to be performed is the analysis of the primary endpoint among subjects with low Allo-S levels
- The seizure frequencies during the titration and maintenance phases will not be analyzed separately
- The time points for the efficacy, exploratory, and quality of life endpoints will be at Weeks 21, 34, 52, and every 16 weeks thereafter of open-label treatment relative to the 6-week prospective baseline phase. For the seizure endpoints, this corresponds to the first 4, 17, 35, 51, etc. weeks from the start of the OLE phase
- The differences between the DB treatment groups in the percent changes from baseline of the 28-day seizure frequencies will not be tested for statistical significance
- No PP analyses will be performed
- If a subject prematurely discontinues from the OLE phase, the EEG comparison to baseline at the Final OL/Taper Visit cannot be reassigned for analysis purposes since the EEG is performed only at that visit in the OLE phase; hence the tabulation at that visit will include all the subjects, regardless of whether they discontinued. (Taper Visit assessments among the subjects who prematurely discontinue from the DB phase are reassigned if possible; if they cannot be reassigned then they are not tabulated.)

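### SAP 9.1 leaves an adverse event on the first open-label dosing day out of both phase-specific AE tables, and the Day 28 example in SAP 7.1.1 contradicts its own 32-day rule

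*SAP*

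**What the plan says.** **AE tables (SAP 9.1).** A treatment-emergent AE (TEAE) "is defined as an AE that starts or worsens on or after the first dosing day of study drug". Of the DB tables the section says "they will not include any AEs starting or worsening on or after the first dosing day of the OLE phase". Of the OLE-only tables it says "The summarizations over just the OLE phase will include TEAEs that start or worsen after the first day of the OLE phase". A third summary covers the entire study from the first ganaxolone dosing day, but "the classification by the DB treatment applies only for the OLE phase summary". All AEs are listed.

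Partial AE start dates can be set to the first OLE dose. Where only the day is missing, the first choice is the first dose date, "else first dose date of the OLE if the year and month are the same". Parallel rules cover a start date with only the year known, and one with the month missing but year and day present. There is an override: "If an imputed start date is later than the stop date, then the stop date (after any needed imputations) will be used" in place of the imputed start.

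**Taper Visit rule (SAP 7.1.1).** For a subject who leaves the study early, Taper Visit data move to the next visit that schedules the assessment, provided its scheduled day is no more than 32 days away. The section places Visit 4 (Week 9) on Study Day 64 and Visit 5 (Week 17) on Study Day 120. It then states that a Taper Visit on Day 28 falls in the window of no scheduled visit and is not reassigned. SAP 9 applies the same rule to safety assessments. Data not reassigned are listed but not tabulated.

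**The concern.** The two AE sentences should meet at one boundary. One excludes the first OLE dosing day from the DB tables and the other excludes the same day from the OLE-only tables. For former placebo subjects it is the first day on ganaxolone, and the OLE-only tables are the only OLE AE tables classified by prior arm. Programmed as written, they undercount.

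The Day 28 example gives a programmer an answer opposite to the rule it illustrates. Following the example would drop the Taper Visit laboratory tests, vital signs, ECG and global ratings of a subject who left the study on such a day in titration from the Week 5 tables.

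**Working it through.** **1. AE boundary.** Let day 0 be the first OLE dosing day, and apply the SAP 9.1 sentences literally.

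| AE starts or worsens | DB table (day < 0) | OLE-only table (day > 0) | OLE-only table if day ≥ 0 |
|---|---|---|---|
| Day −1 | in | out | out |
| Day 0 | out | out | in |
| Day +1 | out | in | in |

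This takes the first day of the OLE phase to be the first OLE dosing day. The SAP supports that elsewhere. In 7.1, DB seizure data run "up to the day before the first dose of OLE treatment for those who do". In 7.2, "The post-baseline seizure endpoints will be derived starting from the first dosing day of OLE treatment". Section 6 counts OLE concomitant medications from the first OLE dosing day inclusive. Section 9.1 itself, in its DB sentence, equates the OLE phase with that day onward.

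The entire-study summary starts on the first ganaxolone dosing day. For a former placebo subject that is day 0, so the event is counted there, though without the split by prior arm.

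**2. Partial dates that land on day 0.** Three patterns are imputed to the first OLE dose date:
- the day is missing, and month and year match the OLE start;
- only the year is known, and the OLE starts in a later calendar year than the first dose;
- the month is missing but year and day are present, which is treated like the previous pattern.

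In each case the AE reaches the gap only if its stop date, after imputation, is absent or not before day 0. Illustration with assumed dates: first dose 16 Feb 2019, first OLE dose 15 Jun 2019, AE start June 2019 with the day missing. With a stop date of 10 Jun, the override sets the start to 10 Jun and the AE is in the DB table. With a stop date of 20 Jun, or none, the start is 15 Jun and the AE is in neither phase table.

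**3. Taper Visit example.** Under the SAP 2.1 convention, Week w is Study Day 7w + 1.
- The plan's own figures reproduce. Visit 4: 7 × 9 + 1 = 64. Visit 5: 7 × 17 + 1 = 120. For its Day 100 example, 120 − 100 = 20 (inside) and 100 − 64 = 36 (outside).
- Visit 3 (Week 5): 7 × 5 + 1 = 36.
- From Day 28: Visit 3 is 36 − 28 = 8 days away (inside), Visit 4 is 64 − 28 = 36 (outside), Visit 5 is 120 − 28 = 92 (outside).
- Reach of the rule: 36 − 32 = 4, so Taper Visits on Days 4 to 28, which is 25 of the 28 titration days, map to Visit 3 for assessments scheduled there.
- For assessments whose next scheduled visit is Visit 5, such as urinalysis and weight, 92 > 32, so no reassignment is the correct result.
- Visit 3 has a window of ±3 days, Days 33 to 39, so a subject at Day 28 cannot already have completed it.

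**The case against.** The best case on the other side is that the AE phrase corrects itself. SAP 6, 7.1, 7.2 and the DB sentence of 9.1 all put the first OLE dosing day in the OLE, and SAP 2.1 sends events after OLE entry to the OLE outputs. A careful programmer would see one stray phrase. It probably is a drafting slip, but SAP 2.1 allows exceptions where indicated, and 9.1 is the specific rule for these tables, so the other sections do not override it.

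A reader might infer that AEs on first ganaxolone exposure disappear for former placebo subjects. The documents do not support that: the entire-study summary starts on that same day for them, and the listings hold every AE. The day also carries only the lowest titration step. A reader might also think every AE with a partial date in the OLE start month is lost; the stop-date override keeps those that ended before the first OLE dose in the DB table.

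On the Taper Visit, one could say that the rule governs and the example only illustrates. That holds for the rule. One could also read the example as continuing the preceding one, in which Visit 3 was completed; the Visit 3 window rules that out at Day 28.

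**Conclusion.** Both defects stand, as minor wording errors.

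**AE tables.** An AE starting or worsening on the first OLE dosing day is missing from both phase-specific tables, and what is lost is its count in the tables split by prior arm. The size is one calendar day per subject entering the OLE, plus the partial-date AEs described. No event count can be given. This rests on reading the first OLE day as the first OLE dosing day.

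**Taper Visit example.** The 32-day rule stands and the example is false for any assessment scheduled at Visit 3. It would be tempting to call the rule itself faulty or to see a risk to Week 17 results. Neither follows: Day 28 maps only to Visit 3, so the effect stops at descriptive Week 5 tables. Few subjects should be affected, because under Protocol 4.5 those who only stop drug in the DB phase remain in follow-up.

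Neither part affects the primary endpoint, a Week 17 result or the listings.

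**What to change.** **SAP 9.1.** Start the OLE-only summary with TEAEs that begin or worsen on the first OLE dosing day, inclusive, matching the cut-off already used for the DB tables. The two phase tables then cover each day once.

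Confine this to AEs and leave SAP 2.1 alone. Protocol 6.2.3 starts OLE dosing at the end of Visit 5, so a general date cut-off could move that day's Week 17 DB assessments into the OLE. On the same assumption about timing there is a small downside: an AE earlier that day, before the first OLE dose, counts as OLE. That agrees with the SAP's TEAE definition, which works by dosing day, and the DB tables already exclude the day.

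**SAP 7.1.1.** State that a Day 28 Taper Visit is reassigned to Visit 3 (Day 36) for assessments scheduled there, and is not reassigned for those next due only at Visit 5. If an example of complete non-reassignment is wanted, Day 75 after a completed Visit 4 works (120 − 75 = 45 days to Visit 5). The sentence must then refer to subsequent visits only, because Day 75 is 75 − 64 = 11 days after Visit 4 and would otherwise be false in the same way.

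The cost is one phrase in 9.1 and a reworded example in 7.1.1. Data collection and the DB AE tables do not change.
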